5.8 Post-Treatment Follow-Up

- 1) Study participants will be contacted by telephone at the end of first month post-treatment for general health
- 2) All study participants will have routine follow-up as we do for the PluSS study participants through mails on an annual basis, to fill out a follow-up questionnaire for the diagnosis of lung cancer or any other cancer or vital status (filled out by the next-of-the-kin).

6. STUDY CALENDAR

		Stage 1		Stage 2 (after randomization)						Post-treatment		
		Pre-clinical	#1	#1	#2	#2	#3	#4	#5	#6	Phone	Mail
Clinical visit	Targeted Date			Day 0*	Day 90±14	Day 180±14	Day 270±14	Day 360±14	Day 367±10		1 mo. after	1 yr. after
Eligibility Screening Form	Phone Interview											
MAIL OUT FORMS												
Locator Form	(mail)	(Rec)										
Baseline Questionnaire	(mail)	(Rec)						(mail)		(Rec)		
Cruciferous Vegetable intake form (compliance)					X	X	X	X		X		
SIGN CONSENT FORM	(PluSS PID)	X										
Assign subject ID (SF-Seq #)†		SF-001 SF-002 ...										
PHYSICAL EXAM												
Vitals, weight & height		X			X	X	X	X		X		
CO test		X			X	X	X	X		X		
O2 test		X										
Spirometry (PFT)		X			X	X	X	X		X		
Urinary Pregnancy Test		X										
BLOOD (for Screening or AE Monitoring)												
CBC/platelets		X				X	X	X		X		
Chemistry panel & LFT		X				X	X	X		X		
BRONCHOSCOPY												
Bronchial biopsy			X							X		
Bronchial brushing			X							X		
Bronchoalveolar lavage			X							X		
INCLUSION/EXCLUSION FORM	(X)	(X)	(X)									
TREATMENT ASSIGNMENT (TA-Seq #)‡				TA-001 TA-002 ...								
Provide study tablets (for 3 months)				X	X	X	X					
Pill count in returned bottles					X	X	X			X		
RESEARCH SAMPLES												
Blood					X	X	X	X		X		
Nasal brushing					X	X	X	X		X		
Spot urine					X	X	X	X		X		
AE ASSESSMENT FORM					X	X	X	X		X		
COMPENSATION		\$50	\$500	\$50	\$50	\$50	\$50	\$500	\$500			
Provide parking ticket		X	X	X	X	X	X	X	X			
FOLLOW-UP											X	X
General health											X	X
Lung cancer											X	X
Any cancer											X	X

* Day 0 is when the subject is given a treatment assignment number.

† Study subject ID is assigned right after the consent form is signed by a potential eligible subject. This number will be used for the entire study and all forms and sample collection sheets.

‡ Treatment assignment number is TA-sequential # of subjects entering into stage 2 of the study. the TA # randomly determines the subject's treatment arm..

7. ADVERSE EVENTS: LIST AND REPORTING REQUIREMENTS

7.1 Adverse Events and Risks

Adverse event (AE) monitoring and reporting is a routine part of every clinical trial. The safety reports will be coded using current versions of Medical Dictionary for Regulatory Activities (MedDRA). Toxicity severity will be reported using National Cancer Institute's Common Terminology Criteria for Adverse Events (CTCAE) term and grade: The descriptions and grading scales found in the revised NCI CTCAE version 4.0 will be utilized for adverse event reporting. All appropriate treatment areas should have access to a copy of the CTCAE version 4.0. A copy of the CTCAE version 4.0 can be downloaded from the CTEP web site (http://ctep.cancer.gov/protocolDevelopment/adverse_effects.htm).

7.1.1 Adverse Events for Broccoli Sprout Preparation Avmacol®

There is no recognized risk from administration of Avmacol® tablets. The previous studies using broccoli sprout beverages in humans reported that the most common adverse events (AEs) or complaint by study participants was bad taste. As a tablet formulation, Avmacol will overcome the bad taste. Other expected AEs in gastrointestinal system are nausea and flatulence. Table 3 summarizes reported AEs in previous studies involved more than 500 study subjects.

There may be adverse events or side effects that are currently unknown. Everyone taking part in the study will be monitored carefully for any side effects, including routine physical examinations, complete blood count (CBC), blood chemistry including liver function test, and food intolerances. All AEs and toxicity measures will be evaluated as one of the objective of the present study.

Table 3. Summary of Reported Adverse Events (AEs) in Studies Using Sulforaphane or Sulforaphane Precursor Glucoraphanin in Humans

Study (reference)*	Design	Subjects	Dose*	Treatment duration	AEs																		
Kensler et al(32)	Randomized placebo-controlled phase 2 study	200 healthy volunteers	400 µmol glucoraphanin (GR)/day in hot water infusion of broccoli sprouts	14 days	No reported AEs																		
Shapiro et al(31)	Randomized placebo controlled phase I study	12 healthy volunteers	75-100 µmol GR/day	7 days	No clinical AEs; No abnormal chemistry test results. 2/12 subjects had ALT >1x ULN (grade 1 toxicity). Note: ALT level rose for all subjects including placebo-treated ones																		
Corblatt et al(29)	Single arm study	8 women undergoing elective mammoplasty	150 µmol SF	Single dose	Well tolerated, no any AEs or complications																		
Egner et al(46)	Randomized placebo-controlled phase 2 study	50 healthy volunteers	Broccoli sprout extract (BSE) beverage: 800 µmol GR/day	7 days	No AEs observed																		
Egner et al(17)	Randomized placebo-controlled phase 2 study	267 healthy volunteers	BSE beverage: 600 µmol GR + 40 µmol SF per day	84 days	10 participants (6 in BSE and 4 in placebo arm) reported grade 1 AEs: bad taste and mild stomach discomfort. One subject (in BSE) reported vomiting. Clinical values of 13 analytes of blood chemistry and liver function test for all participants at the last day of the intervention were all normal.																		
Atwell et al(16)	Randomized double-blind placebo-controlled phase 2 study	54 women with abnormal mammograms and scheduled for breast biopsy	BSE BroccoMax: 180 mg [= 518 µmol] GR/day	2-8 weeks	No difference in AEs between two groups 
  
 AEs	BroccoMax	Placebo	
   
 Bloating	5/27	5/27	
 
 Gas/Flatulence	1/27	4/27	
 
 Diarrhea	1/27	2/27	
 
 Others	5/27	7/27	
 
 All	8/27	9/27	
  
	AEs	BroccoMax	Placebo	Bloating	5/27	5/27	Gas/Flatulence	1/27	4/27	Diarrhea	1/27	2/27	Others	5/27	7/27	All	8/27	9/27
AEs	BroccoMax	Placebo																					
Bloating	5/27	5/27																					
Gas/Flatulence	1/27	4/27																					
Diarrhea	1/27	2/27																					
Others	5/27	7/27																					
All	8/27	9/27																					
Bauman et al(59)	Singe arm study	10 healthy volunteers	BSE beverage: R1: oral 600 µmol GR/day R2: oral 150 µmol SF/day R3: oral rinse 150 µmol SF for 5 minutes, and expectorated	Three 5-day intervention	No AEs reported																		

7.1.2 Risks Associated with Study Procedures

7.1.2.1 Bronchoscopy

Bronchoscopy is very safe, but no procedure is entirely free of potential risk. The following is a description of the risks of the procedure. In recent publications, the incidence of serious complications was less than 0.05% (5 in 10,000) in over 23,000 bronchoscopies. Local discomfort (coughing, gagging and soreness of your nose and throat) are frequently unavoidable but can be greatly diminished with adequate anesthesia. Bronchitis is common after bronchoscopy and may resolve spontaneously or with antibiotic treatment. Nosebleed, wheezing (about 1% chance), a decrease in blood oxygen content of approximately 10% for approximately one half hour, low grade fever (less than a 5% chance), and lung infection (pneumonia) in less than 0.1% and slight expectoration of small flecks of blood for 24 hours after the procedure (as a result of minor trauma to the bronchial lining) may occur. More serious complications such as major bleeding, lung collapse, vocal cord and bronchial spasm, and cardiac irregularity have been reported but are very rare. Since the patient will be medicated for this procedure they will need to make arrangements for someone to drive them home.

A Bronchoscopy Patient Communication Log Form is attached (Appendix 9) to follow-up the patients after the bronchoscopy is performed. Patients are called within 24 hrs., 72 hrs., and instructed to call within 30 days, if febrile, or with increased sputum production, or increasing shortness of breath or any perceived deterioration of respiratory condition.

7.1.2.2 IV Infusion During Bronchoscopy

An intravenous needle will be placed in the subject's arm for the infusion of fluids. The subject can expect to experience some pain at the moment the needle goes into the arm. In addition to this momentary pain, there will be the minor discomfort of having the needle taped in the arm. In about 10 percent of cases small amount of bleeding under the skin will produce a bruise (hematoma). The risk of temporary clotting of the vein is about 1 percent, while the risk of infection of a hematoma or significant external blood loss is less than one in 1,000. In order to minimize these discomforts, only trained doctors and technicians will be permitted to place the intravenous line.

7.1.2.3 Venous Blood Collection

An intravenous needle will be used to collect blood samples from the subject's arm. The collected blood samples will be used for clinical blood tests (CBC and chemistry) for subject's general health and for research use. The subject can expect to experience some pain at the moment the needle goes into the arm. In about 1-2 percent of cases small amount of bleeding under the skin will produce a bruise (hematoma). The risk of temporary clotting of the vein is about less than one percent, while the risk of infection of a hematoma or significant external blood loss is less than one in 1,000.

In order to minimize these discomforts, only trained clinical research nurses or technicians will be permitted to place the intravenous line.

7.1.2.4 Nasal brushing

Nasal cell scraping may be associated with pressure, pain or minor bleeding. The patient may feel some discomfort and nasal sore after nasal brushings. Nasal bleedings are minor and can be stopped after holding the nose for a few minutes.

7.1.3 Violation of Privacy and Loss of Confidentiality

Violation of privacy and loss of confidentiality are both risks to which research participants are exposed. The possibility of these risks increases when protected health information is collected.

7.2 Definitions of Adverse Events

Adverse event: Any untoward medical occurrence associated with the use of a drug in humans, whether or not considered drug related.

Life-threatening adverse event or life-threatening suspected adverse reaction: An adverse event or suspected adverse reaction is considered “life-threatening” if, in the view of either the investigator or sponsor, its occurrence places the patient or subject at immediate risk of death. It does not include an adverse event or suspected adverse reaction that, had it occurred in a more severe form, might have caused death.

Serious adverse event or serious suspected adverse reaction: An adverse event or suspected adverse reaction is considered “serious” if, in the view of either the investigator or sponsor, it results in any of the following outcomes: death, a life-threatening adverse event, inpatient hospitalization or prolongation of existing hospitalization, a persistent or significant incapacity or substantial disruption of the ability to conduct normal life functions, or a congenital anomaly/birth defect. Important medical events that may not result in death, be life-threatening, or require hospitalization may be considered serious when, based upon appropriate medical judgment, they may jeopardize the patient or subject and may require medical or surgical intervention to prevent one of the outcomes listed in this definition. Examples of such medical events include allergic bronchospasm requiring intensive treatment in an emergency room or at home, blood dyscrasias or convulsions that do not result in inpatient hospitalization, or the development of drug dependency or drug abuse.

Suspected adverse reaction: Any adverse event for which there is a reasonable possibility that the drug caused the adverse event. For the purposes of IND safety reporting, “reasonable possibility” means there is evidence to suggest a causal relationship between the drug and the adverse event. Suspected adverse reaction implies a lesser degree of certainty about causality than adverse reaction, which means any adverse event caused by a drug.

Unexpected adverse event or unexpected suspected adverse reaction: An adverse event or suspected adverse reaction is considered “unexpected” if it is not listed in the investigator brochure or is not listed at the specificity or severity that has been observed; or, if an investigator brochure is not required or available, is not consistent with the risk information described in the general investigational plan or elsewhere in the current application, as amended. For example, under this definition, hepatic necrosis would be unexpected (by virtue of greater severity) if the investigator brochure referred only to elevated hepatic enzymes or hepatitis. Similarly, cerebral thromboembolism and cerebral vasculitis would be unexpected (by virtue of greater specificity) if the investigator brochure listed only cerebral vascular accidents. “Unexpected,” as used in this definition, also refers to adverse events or suspected adverse reactions that are mentioned in the investigator brochure as occurring with a class of drugs or as anticipated from the pharmacological properties of the drug, but are not specifically mentioned as occurring with the particular drug under investigation.

7.3 Reporting Adverse Events to the Responsible IRB

In accordance with applicable policies of the University of Pittsburgh Institutional Review Board (IRB), the Sponsor-Investigator will report, to the IRB, any observed or volunteered adverse event that is determined to be 1) *associated with the investigational drug or study treatment(s)*; 2) *serious*; and 3) *unexpected*. Adverse event reports will be submitted to the IRB in accordance with the respective IRB procedures.

Applicable adverse events will be reported to the IRB as soon as possible and, in no event, later than 10 calendar days following the sponsor-investigator’s receipt of the respective information. Adverse events which are 1) *associated with the investigational drug or study treatment(s)*; 2) *fatal or life-threatening*; and 3) *unexpected* will be reported to the IRB within 24 hours of the Sponsor-Investigator’s receipt of the respective information.

Follow-up information to a reported adverse event will be submitted to the IRB as soon as the relevant information is available. If the results of the Sponsor-Investigator’s follow-up investigation show that an adverse event that was initially determined to not require reporting to the IRB does, in fact, meet the requirements for reporting; the Sponsor-Investigator will report the adverse event to the IRB as soon as possible, but in no event later than 10 calendar days, after the determination was made.

7.4 Data Safety and Monitoring Board (DSMB)

We will create an institutional internal independent DSMB committee to review the safety and toxicity data that is submitted by the study statistician every 12 months. The definitions of adverse events are described in section 7.3. Specifically we will collect expected and unexpected adverse events in Adverse Events Recording Form

(Appendix 8). The DSMB will review the frequency, grade and relationship to the study agent in the treatment group compared with the placebo group.

8. BIOSPECIMENS, BIOMARKER, AND SPECIAL STUDIES

8.1 Human Biospecimen Collection

8.1.1 Endobronchial Biopsies

Endobronchial biopsy samples will be collected during bronchoscopies. The procedure will be carried out by [name] (Co-PI) using Narrow Band Imaging (NBI) white-light bronchoscopy. Up to 3 biopsies will be taken from each of six predetermined sites: upper lobe orifices and superior segment orifices (left and right), carina between left upper lobe division and lingular orifices and right middle lobe orifice. In addition, biopsies will be taken from any sites that appear suspicious. On the post-treatment bronchoscopy, sites that had a mild or greater grade of dysplasia at baseline will be re-biopsied.

Of the 3 tissue blocks per biopsy site. All biopsy samples will be put in an ice-cooled box and sent to [name] (Co-I) for processing. Bronchial biopsies will be fixed in 10% neutral-buffered formalin for 6 to 24 hours, embedded in paraffin and routinely processed in the CLIA/CAP certified histology laboratory at the Department of Anatomic Pathology. One section per tissue block will be processed for routine hematoxylin-eosin (H&E) staining for histological evaluation and 10 unstained slides will be cut for immunoperoxidase studies.

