5. TREATMENT PLAN AND STUDY PROCEDURES

5.1 Pre-Treatment Evaluation

Pretreatment tests should be performed within 90 days prior to the randomization.

- 1) Signed informed consent
- 2) Questionnaire data collection on patient's characteristics and smoking history.
- 3) Physical exam including height, weight, vitals and SWOG performance status.
- 4) FEV1/FVC
- 5) Blood oxygen saturation
- 6) Expired Carbon Monoxide
- 7) Laboratory analysis including CBC and serum chemistries such as total bilirubin, AST, ALT, BUN, creatinine, .
- 8) Baseline bronchoscopy: Prior to randomization, all participants will undergo a bronchoscopy at the Endoscopy Suite at the UPMC Shadyside Hospital. The procedure will be carried out by [name] (Co-PI) using Narrow Band Imaging (NBI) white-light bronchoscopy. The patient's nose, throat, vocal cords and windpipe are sprayed with Lidocaine (numbing medicine) to help keep patient from coughing and to numb patient's airways. During the procedure, [name] will perform a complete airway examination including visualization of the vocal cords, trachea, main carina, and orifices of the sub-segmental bronchi to the extent that it is visible without causing trauma to the bronchial wall. Biopsy samples will be collected at the pre-determined sites. Some of these biopsies will be used for the pathological examination. Any patients with lung cancer or carcinoma in situ will be ineligible for the present study. We will inform subjects the abnormal biopsy results and provide appropriate counseling from qualified medical personnel.

Since the clinical significance of moderate or severe dysplasia is unknown and no effective treatment available, we will not conduct additional clinical procedure or intervention on these patients beyond routine follow-up and care. The patients with dysplasia will be monitored at each clinical visit (once every three months during the treatment period) according to the study protocol. At the end of study period, another biopsy at the same site of initial locations that show dysplasia will be performed to evaluate the change (progress, regress or no change) of these lesions detected at baseline biopsy. This is one of the primary outcome measures for the proposed study. After the completion of the study, the patients will continue to receive routine medical care including annual CT screening if eligible.

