5.5 Clinical Visits

Besides two clinical visits in stage 1 of the study for eligibility screening, all eligibility study participants will begin taking the study tablets at visit 1 of stage 2 of the study and return to the study clinic at the end of months 3, 6, 9, and 12 (the end of treatment period). At each clinical visit, the clinical research nurse/assistant will conduct the following:

- 1) Exam the subject's diary for dosing and timing of intake of test tablets, and keep the diary in subject's folder.
- 2) Count and record the remaining tablets given.
- 3) Provide new study tablets that will supply the next 3 months.
- 4) Study participant will turn in the self-administered questionnaire for recording his/her intake of cruciferous vegetables in the past 3 months using a dietary frequency questionnaire (Appendix 5).
- 5) Collect blood, spot urine and nasal brushing samples
- 6) Conduct pulmonary function test: FEV1/FVC
- 7) Collect safety and toxicity measures at each clinical visit (once every 3 months) during the 12-month treatment period:
 - a) Collect adverse events (AEs) using the AE Recording Form (Appendix 8)

- b) Conduct physical examination including body weigh, height, and vitals by a registered nurse and record the results in the patient's study file
- c) Laboratory evaluation: CBC with platelets and differential, chemistry panel including liver function testing.
- 8) Only at the end of treatment period, bronchoscopy will be performed on the patient using the same procedure as described above in 5.1(8) and bronchial biopsies and lavage samples collected (stage 2- visit 5).

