8.2 Biomarkers

8.2.1 Histology (atypia)

It has long been established that abnormal bronchial histology (atypia) is associated with cigarette smoking and increased risk for lung cancer. In a follow-up study of a high-risk cohort of subjects with endoscopic biopsies, persistence of bronchial dysplasia was associated significantly with a 7-fold increased risk of developing NSCLC (adjusted hazard ratio = 7.8, 95% CI 1.6-39.4) (18). All bronchial biopsies

for histopathological evaluation will be formalin fixed, paraffin embedded, and H&E stained for subsequent morphologic evaluation and classification. Biopsies will be classified into 1 of 8 categories as defined by the World Health Organization (WHO) classification (74) and assigned a score according to the following system: 1= normal; 2= reserve cell hyperplasia; 3 = squamous metaplasia; 4 = mild dysplasia; 5 = moderate dysplasia; 6 = severe dysplasia; 7 = carcinoma in situ; and 8 = invasive carcinoma. Subjects with baseline score 7 or 8 are ineligible for the proposed study. All biopsies will be graded by the study pathologist ([name]) in a blinded fashion as to treatment group.

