9.1 Statistical Analysis for histological responses

Endobronchial histology scores will be first summarized within each bronchoscopy by using 3 separate endpoint measures pre and post treatment respectively: 1) dysplasia index (DI, number of biopsies with dysplasia/total number of biopsies x 100), 2) average of all histological scores (all biopsies scores/number of biopsies), and 3) worst biopsy score. The 3 summary end points will be analyzed within 4 different biopsy site groupings: all biopsies, biopsies from the 6 standard endobronchial sites only, site-matched biopsies from both bronchoscopies, and site-matched biopsies where the baseline biopsy is non-normal. For each patient, the mean of each of endpoints separately for each of biopsy site groupings pre and post treatment are then calculated. The primary endpoint is the dysplasia index (DI), which has a binomial distribution with at least 6 “trials” (i.e., 6 predetermined biopsy sites), and will be analyzed by generalized estimating equations (GEE) that constrains average baseline DI to be the same for both treatment and placebo groups, and tests whether average follow-up DI differs between the SF treatment and placebo groups. All other endpoints and biopsy site groupings are secondary endpoints. The primary analysis for the average and worst dysplasia scores will be a linear regression that assesses the difference in post-treatment scores by the two treatment groups, controlling for the same scores at pre-treatment. This analysis of covariance (ANCOVA) approach has optimal efficiency in a study design to assess the pre- and post-treatment measures with high within-subject correlation due to repeated measures (80). No interim analyses for futility or superiority will be performed, other than ongoing safety monitoring.

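### Lower-grade extra biopsy sites enter two secondary site-matched groupings only if they look suspicious again at month 12 (minor)

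*Combined protocol and SAP*

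**What the plan says.** **Sampling.** Section 8.1.1 gives three rules. For the standard sites: "Up to 3 biopsies will be taken from each of six predetermined sites". For the rest of the airway: "In addition, biopsies will be taken from any sites that appear suspicious". For the second bronchoscopy: "On the post-treatment bronchoscopy, sites that had a mild or greater grade of dysplasia at baseline will be re-biopsied". Section 5.1 uses the same dysplasia threshold: "another biopsy at the same site of initial locations that show dysplasia will be performed". Section 5.5, item 8, says the month-12 bronchoscopy follows the baseline procedure and adds no further re-biopsy rule.

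**Grading.** Section 8.2.1 scores the lower grades as "1= normal; 2= reserve cell hyperplasia; 3 = squamous metaplasia; 4 = mild dysplasia". Non-normal therefore begins at 2 and dysplasia at 4.

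**Analysis.** Section 9.1 summarises dysplasia index (DI), average score and worst score within four site groupings. Two of these are "site-matched biopsies from both bronchoscopies, and site-matched biopsies where the baseline biopsy is non-normal". Their status is clear: "All other endpoints and biopsy site groupings are secondary endpoints".

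**The concern.** The threshold that guarantees a follow-up biopsy (score 4) is not the one that defines the site-matched groupings (any score, or score 2 and above). The gap concerns extra sites, meaning sites outside the six predetermined ones that were biopsied at baseline because they looked suspicious. If such a site scored 1 to 3, no written rule brings it back at month 12 except that it looks suspicious again.

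Its presence in a matched analysis then depends on something seen after randomisation and probably related to the outcome. A metaplastic extra site that has cleared tends to go unobserved, while one that has persisted or progressed tends to be observed. The non-normal-baseline grouping is a natural place to look for regression of hyperplasia and metaplasia, and at extra sites that regression may be selectively missed.

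**Working it through.** **1. The plan's own figure.** The nearest stated figure is 80% power for DI (section 9.1: 60 completers, 6 biopsies each, 22% versus 11%, two-sided 0.05). Take the placebo follow-up DI as 22% and treat biopsies as independent, so there are 30 × 6 = 180 per arm. The pooled proportion is 0.165. The null standard error is √(2 × 0.165 × 0.835 / 180) = 0.0391. The alternative standard error is √((0.22 × 0.78 + 0.11 × 0.89) / 180) = 0.0387. Then z = (0.11 - 1.96 × 0.0391) / 0.0387 = 0.86, giving power 80.5%. A 4,000-trial simulation of a binomial model adjusted for baseline DI gave 79.8%. The figure reproduces. It rests on six biopsies per patient and does not use extra sites.

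**2. The rules side by side.**

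| Site and baseline score | Follow-up biopsy set by | Site-matched grouping | Non-normal-baseline grouping |
|---|---|---|---|
| Predetermined, any | site list | in | in if score ≥ 2 |
| Extra, 4-6 | baseline dysplasia rule | in | in |
| Extra, 2-3 | month-12 appearance | in only if suspicious again | in only if suspicious again |
| Extra, 1 | month-12 appearance | in only if suspicious again | not applicable |

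Only the last two rows are affected. The documents give neither the number of such sites nor any link between appearance and histology, so steps 3 and 4 use assumed values throughout.

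**3. Mean score at extra sites with baseline 2-3.** Let follow-up grade be normal (1), unchanged (2.5) or dysplastic (4), with probabilities 30/50/20% on placebo and 50/40/10% on SF. The true means are 0.3 + 1.25 + 0.8 = 2.35 and 0.5 + 1.0 + 0.4 = 1.90, a difference of -0.45. Let s be the chance of looking suspicious at each follow-up grade. The observed mean is Σ(p·s·grade) / Σ(p·s), and the matched share is Σ(p·s).

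| s (normal / unchanged / dysplastic) | Matched share, placebo / SF | Observed mean, placebo / SF | Observed difference |
|---|---|---|---|
| 50 / 75 / 100% | 73% / 65% | 2.60 / 2.15 | -0.45 |
| 20 / 50 / 90% | 49% / 39% | 2.87 / 2.46 | -0.41 |
| 10 / 40 / 90% | 41% / 30% | 3.05 / 2.70 | -0.35 |
| 0 / 50 / 100% | 45% / 30% | 3.17 / 3.00 | -0.17 |

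Both means rise in every row. The difference ranges from unchanged to clearly diluted.

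**4. DI at the same kind of site.** Let true follow-up dysplasia p be 30% on placebo and 15% on SF, with probability of biopsy a if dysplastic and b if not. Observed DI = pa / (pa + (1 - p)b).

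- a = 70%, b = 20%: 0.21/0.35 = 60.0% versus 0.105/0.275 = 38.2%, 21.8 points apart.
- a = 50%, b = 30%: 0.15/0.36 = 41.7% versus 0.075/0.33 = 22.7%, about 19 points apart.
- a = 90%, b = 10%: 0.27/0.34 = 79.4% versus 0.135/0.22 = 61.4%, about 18 points apart.

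The true gap is 15 points. The observed odds are [p/(1 - p)] × (a/b), so a/b cancels between arms. The odds ratio is (0.30/0.70) / (0.15/0.85) = 2.43 before selection and 2.43 in all three cases.

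**5. Worst score.** A maximum over fewer sites cannot exceed the maximum over all of them. Losing cleared extra sites therefore leaves a patient's worst score unchanged.

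**The case against.** Much of the case on the other side stands.

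- **Treatment effect on DI.** A reader might infer from the inflated DI levels that the treatment effect is distorted. On the odds-ratio scale it is not, for these sites alone, provided appearance relates to histology in the same way in both arms. The logit scale is itself an assumption, because section 9.1 specifies a binomial outcome but no link. Pooling with predetermined sites breaks the exact equality, by an amount that needs the unknown share of extra sites.
- **Worst score.** A reader might infer that all three summaries are overstated. Step 5 shows that worst score is not, by this route. The one exception is a patient whose only non-normal baseline site was an unmatched extra one. That patient leaves the non-normal grouping altogether, and the documents do not show how often this would occur.
- **Validity.** A reader might infer that randomisation is undone or false positives rise. Section 9 describes a double-blind trial and section 8.2.1 blinds the pathologist. With no treatment effect, selection works alike in both arms, so false positives should not rise.
- **Strength of the link.** These extra sites were biopsied because they looked suspicious and yet showed no dysplasia, so appearance may be a weak guide there. In step 4 the bias vanishes as a approaches b.
- **Meaning of site-matched.** Section 9.1 does not promise every baseline site; a matched site is one sampled twice. That is correct, but being sampled twice is exactly what depends on month-12 appearance.
- **The all-biopsies grouping.** It also contains appearance-driven biopsies, and the fix below leaves it alone.

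What survives is the mismatch in thresholds, the upward bias in absolute levels if appearance tracks histology, and the possible dilution in mean score, which is analysed by linear regression and lacks the odds-ratio protection.

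**Conclusion.** The mismatch is real and minor. Two secondary groupings admit extra sites scored 1-3 at baseline (2-3 in the non-normal grouping) according to their appearance after treatment. If appearance tracks histology, follow-up DI and mean score at those sites are biased upward. The arm difference may be diluted for mean score or shifted in percentage points for DI. Neither size nor net direction can be calculated from the documents, and with few such sites the effect may be small.

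Two stronger readings are not supported. The re-biopsy sentence might be taken to mean that only dysplastic sites are sampled at month 12. Section 8.1.1 describes the six predetermined sites as part of the bronchoscopy procedure, section 5.5 repeats that procedure, and section 9.1 relies on at least six biopsies. The primary endpoint might also be thought biased. Section 9.1 does not name its grouping outright, but it explains the binomial count by the six predetermined sites, which this selection does not touch.

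**What to change.** In section 9.1, before unblinding, limit both site-matched groupings to sites whose follow-up biopsy is set by baseline status: the six predetermined sites plus extra sites with baseline score 4 or more. State that the non-normal grouping then uses score 2 or more at predetermined sites and 4 or more at extra sites. Report the remaining extra sites, including newly suspicious ones, descriptively.

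This is a short text change. It needs no further biopsies and leaves the primary endpoint and power calculation alone. The cost is that a few extra sites leave two secondary groupings and the non-normal grouping carries a mixed threshold. Setting a follow-up sampling rule for every baseline extra site would also close the gap, but whether added biopsies are acceptable is for the investigators.
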